Our overall research goal is to evaluate the clinical utility of preoperative pessary placement as a part of patient counseling or preparation for surgery. In this protocol we aim to increase patient preparedness for surgery, patient satisfaction, and post-operative quality of life in adult women scheduled for surgery for symptomatic pelvic organ prolapse. To accomplish this, following counseling regarding all treatment options for prolapse, we will perform a prospective case-crossover study where 112 subjects who elected for surgical management will utilize a pessary for 1-4 weeks prior to undergoing prolapse surgery.

We propose:

Specific aim 1a: To evaluate concordance of the Patient Global Impression of Improvement Score between vaginal pessary use (assessed prior to surgery) and surgical intervention (assessed at 3 months postoperatively) for women with pelvic organ prolapse. *Hypothesis:* There is a strong correlation between the self-reported Patient Global Impression of Improvement Score following pessary use and surgery, as assessed at 3 months post-operatively.

Specific aim 1b.) To evaluate concordance in symptomatic change in pelvic and voiding symptoms (measured by validated symptom questionnaires) from baseline between pessary use (assessed prior to surgery) and surgical intervention (assessed at 3 months postoperatively). *Hypothesis:* There is a strong correlation between the changes in pelvic and voiding symptoms following pessary use and surgery, as assessed at 3 months post-operatively

Specific aim 2: To evaluate the impact of preoperative pessary use on patient preparedness for surgery (measured by validated questionnaire) as compared between the initial office consultation and following 1-4 weeks of pessary use.

Hypothesis: Preoperative pessary use will increase self-reported preoperative patient preparedness for surgery compared to office counseling alone.

II. Research Strategy

1. Significance:

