C.2. Participants

Study population: The study will be open to women (over age 18) presenting for evaluation and management of symptomatic pelvic organ prolapse at Mayo Clinic (Rochester, MN), who elect to undergo surgical management.

Inclusion criteria: Female patients: 1) older than 18 years of age; 2) with symptomatic pelvic organ prolapse; 3) electing for surgical repair of pelvic organ prolapse (transvaginal or transabdominal) at least 7 days after office consultation. A minimum of one week was chosen as the duration of pessary use, as this was found sufficient in a study evaluating diagnosing occult urinary incontinence with pessary use prior to prolapse surgery;³⁶ 4) who understand and have signed written informed consent for preoperative pessary placement.

Exclusion criteria: Patients that: 1) have previously been managed with a pessary for pelvic organ prolapse; 2) patients undergoing obliterative prolapse surgery (i.e. Colpocleisis), 3) are scheduled for surgery for pelvic organ prolapse less than 7 days after office consultation 4) have an isolated rectocele; 5) have allergies to both latex and silicone; 6) have an active pelvic infection.

C.3. Outcome Assessment

The primary aim (1a) will be assessed using the 7-point Likert scale of the Patient Global Impression of Improvement (PGI-I).^{1, 35} Concordance will be estimated along with a 95% confidence interval. Patient's will be considered treatment success if they answer "much better" or "very much better" on the PGI-I scale.³⁵ The additional primary aim (1b) will be assessed using Lin's concordance correlation coefficient for responses to: Pelvic Organ Prolapse Distress Inventory-6 (POPDI-6) which measures prolapse symptom severity, Pelvic Floor Impact Questionnaire-7 (PFIQ-7) to evaluate patient bother from their bladder/vaginal/bowel symptoms, and the Overactive Bladder Symptom Score (OABSS). The secondary aim will be assessed by evaluating patient responses to a preoperative preparedness questionnaire. Patients will be considered prepared for surgery if they answer "strongly agree" on a 6-point Likert scale, with responses ranging from "strongly disagree" to "strongly agree" to the question: "Overall, I feel prepared for my upcoming surgery."²

C.4. Sample Size Considerations

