Aim 1: Using the 7-point Likert scale of the PGI-I, we anticipate an overall concordance of at least 80% between the within patient ratings following pessary use and 6-weeks following surgery after collapsing the categories into a) much better or very much better, b) a little better, no change, or a little worse, or c) much worse or very much worse. In order to estimate the concordance with a ½ width of the 95% CI of 10% (i.e. 95% CI of 70.8-90.5%), the study will need 62 patients.

Aim 2: Based on a recent study of 79 women who underwent reconstructive pelvic surgery after standard office counseling, 58% strongly agreed that they were prepared for their upcoming surgery.² If we assume that following pessary use, 75% will endorse that they strongly agreed that they were prepared for their upcoming surgery, then the study will have 80% power to detect this difference with a sample size of 84 patients. This calculation was based on two-sided McNemar's test for comparing correlated proportions assuming a mild correlation (0.30) between the paired measures and a type I error of 0.05. Assuming a conservative 25% drop-out rate (failure to wear the pessary or complete follow-up questionnaires) then the study would need to consent 112 patients.

Feasibility: The Division of Urogynecology at Mayo Clinic, Rochester, MN typically performs roughly 1350 surgeries annually (averaged from surgical volume from 1/1/2013 to 1/1/2015). Among those, the four fellowship trained Urogynecologists typically perform roughly 650 prolapse procedures per year. Thus, given the large surgical volume, recruitment for this study is feasible as a single center trial.

C.5. Data Collection

Preoperative demographic data, complete medical and surgical histories, as well as current medications and allergies will be obtained to ensure patients meet inclusion and exclusion requirements. Participants will fill out the following validated questionnaires and questions prior to any intervention and following each

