treatment (pessary and surgery): Pelvic Floor Impact Questionnaires (PFIQ-7),³⁷ Pelvic Organ Prolapse Distress Inventory 6 (POPDI-6),³⁷ and Overactive Bladder Symptom Score (OABSS).³⁸ Thus, questionnaire assessments will be completed at the time of initial consultation, immediately prior to surgery (after pessary use), at 6 weeks postoperatively during office consultation, and via mailed questionnaires and phone interviews at 3 months. Patient preparedness for surgery will be assessed via validated questions after completing the standard office based counseling and signing the surgical informed consent (prior to pessary use), as well as immediately prior to surgery (after pessary use), according to validated questions evaluating self-reported preparedness for pelvic surgery.² Furthermore, following treatment with a pessary (prior to surgery), at 6 weeks and 3 months after surgery patients will complete the Patient Global Impression of Improvement (PGI-I) question.^{1, 35} All adverse events associated with pessary use or surgery will be documented and abstracted.

Baseline characteristics for the patients included in the trial will be reported as median with inter-quartile range for continuous variables and counts with percentages for categorical variables. The percent concordant will be calculated along with the corresponding 95% confidence interval. Given the paired nature of the data (post-pessary vs. post-surgery), differences between the two time points for dichotomous responses will be assessed using McNemar’s test whereas differences between ordinal responses will be assessed using Bowker’s test for symmetry. The correlation between the two time points for summary scores from validated questionnaires (POPDI-6, PFIQ-7, OABSS) will be assessed using Lin’s concordance correlation coefficient. All calculated p-values will be two sided and will be considered significant if < 0.05.

Study Schedule	Initial visit	After pessary use, day of surgery	Surgery	6 wks after surgery (clinic visit)	3 mos after surgery (mailing)
Medical History and Physical	X				
Informed Consent	X				
Pessary Fitting	X				
Preparedness for Surgery	X	X			
PFIQ-7	X	X		X	X
POPDI-6	X	X		X	X
OABSS	X	X		X	X
PGII		X		X	X
Surgery			X		

C.6. Potential limitations of the study design and alternative strategies:

Potential Limitations:

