Carry-Over Effect: This would be encountered if preoperative pessary use changed the pelvic floor in a way that influenced the outcome of surgery. As there is no “wash-out” time from pessary removal to surgery, such an effect would impact the surgical outcome. Given that the pessary is a mechanical change in anatomy of the pelvic floor, we anticipate that with pessary removal there would not be residual impact from the pessary.

Recruitment: As patients would be counseled regarding surgery and pessary use and would have elected for surgery prior to study consent, we could encounter difficulties with recruitment in that patients would need to consent to temporary pessary use. Given the volume of patients seen in our department and the sample size needed, we feel that this should not be prohibitive.

Alternative strategies:

Observational cohort: An alternative strategy would be to compare symptomatic improvements between pessary use and surgery in two separate cohorts of patients, in an observational study. As there would be

significant selection bias in patients that undergo pessary placement rather than surgical correction, this methodology was not preferred.

Randomized clinical trial: A randomized clinical trial could be performed where patients are randomized to preoperative pessary use or proceeding directly to surgery. This approach could potentially minimize the impact of confounding variables. This method was not preferred due to perceived difficulty in recruitment (as patients may have a specific time in which they prefer to have surgery) and difficulty in surgical scheduling.

C.7. Timeframe: (24 months)

For Aim 1, we estimate that it will take 8 months for recruitment of the 62 patients, assuming a recruitment rate of 15% (~54 surgeries for prolapse in our division per month, as estimated by averaging volume from 2013 and 2014). For completion of Aim 2, we estimate that it will take 14 months to recruit the 112 patients for study, assuming a recruitment rate of 15%. Given the surgical volume in our division we anticipate being able to meet the accrual requirements.

	2016							2017											2018					
Study Month	1	2	3	4	5	6	7	8	9	10	11	12	13	14	15	16	17	18	19	20	21	22	23	24
Aim 1																								
Data Collection	x	x	x	x	x	x	x	x																
Data Analysis									x	x														
Manuscript										x	x	x	x											
Aim 2																								
Data Collection	x	x	x	x	x	x	x	x	x	x	x	x	x	x										

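### The primary PGI-I concordance is set at 3 months in Specific aim 1a but at 6 weeks in the C.4 sample-size text, and the C.5 analysis paragraph does not say which visit is primary

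*Combined protocol and SAP*

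**What the plan says.** Specific aim 1a asks for concordance of the PGI-I "between vaginal pessary use (assessed prior to surgery) and surgical intervention (assessed at 3 months postoperatively) for women with pelvic organ prolapse". Its hypothesis repeats the visit, predicting a strong correlation of the "Patient Global Impression of Improvement Score following pessary use and surgery, as assessed at 3 months post-operatively". Aim 1b and its hypothesis also use 3 months.

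C.4, Aim 1, bases the sample size on an expected concordance of at least 80% "between the within patient ratings following pessary use and 6-weeks following surgery after collapsing the categories into" three groups. The target is a 95% CI half-width of 10 points, which gives 62 patients.

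C.3 introduces the outcome as the one for primary aim 1a and then says "Concordance will be estimated along with a 95% confidence interval", without naming a postoperative visit. The data-collection text of C.5 says that "at 6 weeks and 3 months after surgery patients will complete the Patient Global Impression of Improvement (PGI-I) question", and the schedule table agrees. The analysis paragraph of C.5 refers to one postoperative rating only: "Given the paired nature of the data (post-pessary vs. post-surgery".

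C.7 states that for Aim 1 "it will take 8 months for recruitment of the 62 patients, assuming a recruitment rate of 15" percent. It marks Aim 1 data collection in months 1-8 and Aim 1 analysis in months 9-10.

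**The concern.** Two current sections of one document define the same primary quantity at different visits, and the paragraph that should settle the matter treats the postoperative rating as if there were only one. C.4 is also the only section that gives the three-category grouping. An analyst who goes there for the grouping finds it in a sentence that says 6 weeks.

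Both ratings will be in the database. The primary result of aim 1a is a single percentage with a confidence interval, so an unfixed visit leaves room to choose between two percentages after both are known. The visits also differ in how data are obtained: in clinic at 6 weeks, by mail and phone at 3 months. Completeness may therefore differ between them. The plan gives no completion rate by visit.

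**Working it through.** **1. The texts side by side**

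| Section | Postoperative visit for PGI-I concordance |
|---|---|
| Specific aim 1a | 3 months |
| Aim 1a hypothesis | 3 months |
| C.3 | none named; refers to primary aim 1a |
| C.4, Aim 1 | 6 weeks |
| C.5, data collection and schedule | both collected, neither called primary |
| C.5, analysis paragraph | post-surgery only |
| C.7 | none named |

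Only C.4 departs from 3 months, and no section acknowledges the difference.

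**2. Does the visit affect N?**

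Inputs from C.4: p = 0.80, half-width h = 0.10, 95% confidence.

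n = z² p(1−p)/h² = 1.96² × 0.80 × 0.20 / 0.10² = 61.46, rounded up to 62, as stated. The quoted interval of 70.8-90.5% is the Wald interval for 50/62 = 80.6%, that is 80.6 ± 9.8 points. The visit does not enter the formula. With 80% assumed at either visit, 62 rated women give a half-width of 9.96 points.

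Precision depends on the visit only through the number of women rated. As an assumed range, if 0-25% of 62 women lack a 3-month rating, the half-width runs from 9.96 (n=62) to 11.6 points (n=46). With the 84 completers planned for Aim 2 it is 8.6 points.

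**3. How far apart can the two figures be?**

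Both figures use the same post-pessary rating. A woman can be concordant at one visit and discordant at the other only if her postoperative category changes between visits. In women rated at both, the figures therefore differ by at most the share who change, at 1/62 = 1.6 points per woman. The plan gives no such share.

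An illustration on assumptions outside the documents takes true concordance of 80% at both visits and a correlation ρ between a woman's concordant/discordant status at the two visits.

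- SD of the difference = √(2 × 0.80 × 0.20 × (1−ρ)/62), and the mean absolute difference ≈ 0.798 × SD.
- ρ = 0.2: SD 6.4 points, mean absolute difference 5.1 points.
- ρ = 0.9: SD 2.3 points, mean absolute difference 1.8 points.

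Always reporting the higher figure adds half of this on average, about 0.9 to 2.6 points.

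**4. Does the C.7 timetable settle the visit?**

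Inputs: about 54 surgeries a month, 15% recruitment, and 1-4 weeks of pessary use. One week is taken as 12/52 month. I assume even recruitment, surgery straight after the pessary period, and no drop-out.

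- Rate: 54 × 0.15 = 8.1 a month, so 62/8.1 = 7.65 months (the plan says 8).
- Lag from recruitment to the 6-week rating: 7-10 weeks = 1.62-2.31 months.
- Lag to the 3-month rating: 3 months + 1-4 weeks = 3.23-3.92 months.

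| | 6-week rating | 3-month rating |
|---|---|---|
| Last rating, 8 months' recruitment | month 9.6-10.3 | month 11.2-11.9 |
| Last rating, 7.65 months' recruitment | month 9.3-10.0 | month 10.9-11.6 |
| Women rated by end of month 8 (8.1 a month) | 46-51 | 33-38 |

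The Aim 1 data-collection row therefore fits neither visit. It equals the recruitment period: 8 months for Aim 1, and likewise 14 months for Aim 2, where 112/8.1 = 13.8.

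**The case against.** The strongest reply is that the aim governs. The specific aims state 3 months four times, counting aims 1a and 1b and their hypotheses, and C.3 ties the outcome to aim 1a. Six weeks appears once for this endpoint, in a planning assumption. On that view C.4 holds a slip in one phrase and the default is evident. Much of this stands, and it is why 3 months is the recommended visit. It does not close the point, because the C.5 analysis paragraph names no visit and C.4 contradicts the aim within the definition of the primary quantity.

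A reader might infer more, in three ways that the documents do not support.

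- *The visit cannot be determined at all.* This goes too far, given the link from C.3 to aim 1a.
- *C.7 shows that 6 weeks is meant, because the timetable has room for every 6-week rating but not for the 3-month ones.* The data-collection row ends with recruitment and carries no information about follow-up. With the stated 8 months of recruitment, the last 6-week rating can itself fall after month 10.
- *Aim 1 loses precision.* At 8.1 a month, 8.1 × (10 − 3.92) to 8.1 × (10 − 3.23) gives 49-54 women with a 3-month rating by the end of month 10, and a half-width of 10.7-11.2 points at 80%. That arises only if Aim 1 is analysed early on an incomplete set. Enrolment continues for Aim 2, with 84 completers planned.

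It is also fair to say that aim 1a is estimation with no success threshold, so a choice between visits would shift a descriptive figure and reverse no decision.

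**Conclusion.** The inconsistency is real and nothing in the plan resolves it explicitly. Aim 1a says 3 months, C.4 says 6 weeks, both ratings are collected, and C.5 does not name the primary one. Three months is the natural reading. As written, though, a choice between two primary figures remains open until after both are seen.

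The size is modest. N=62 reproduces and holds at either visit if 80% is assumed. The illustrative gain from picking the higher figure, about 0.9-2.6 points, is small against a 10-point half-width. It rests on assumed correlations, and the low correlations behind the larger value are the less plausible ones because both figures share the post-pessary rating. Confidence is high for the mismatch itself and does not extend to any particular size of bias. This is a point to consider, justified mainly by how little the correction costs.

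**What to change.** 1. In C.4, Aim 1, replace 6 weeks after surgery with 3 months after surgery, and confirm that 80% is still the expected concordance there. N=62 then stands.
2. In the C.5 analysis paragraph, state that the primary figure for aim 1a is the percentage of women whose post-pessary and 3-month PGI-I ratings fall in the same one of the three C.4 categories, and that the 6-week figure is secondary. A cross-reference in C.3 would help.
3. In C.7, extend Aim 1 data collection to about month 12 and start the Aim 1 analysis after the last 3-month rating. Tying the start to that event is safer than a calendar month, since the dates above assume no drop-out.

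If the sponsor means 6 weeks, change aim 1a and its hypothesis instead, and still extend Aim 1 data collection to about month 10-11.

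Neither route adds a patient, visit or questionnaire. With 3 months, the Aim 1 analysis moves from months 9-10 to about months 13-14 and its manuscript moves with it, inside the 24-month timeframe. The choice should be recorded before any postoperative PGI-I data are examined.

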Prediction of postsurgical
symptomatic outcomes with
preoperative pessary use

NCT#02680145

08/22/2016

Prediction of postsurgical symptomatic outcomes with preoperative pessary use

Principal Investigator- [name]

Co-Investigator- [name]

Abstract

Pelvic organ prolapse is a highly prevalent and distressing condition for patients. Despite standard office-based consultation many patients report feeling unprepared for surgery. Likewise, in cases of equivocal symptoms, it is difficult to predict the ability of surgery to improve patient's quality of life and meet expectations. Occasionally, some providers utilize a pessary to evaluate the potential role for surgical correction. However, this is an empiric practice, rather than evidence-based. In addition to the evaluation of symptomatic improvement, pessary use in this setting is an important consideration as it may provide a better functional demonstration of the expected postoperative quality of life, compared to office-based discussion. The purpose of this project is to evaluate the potential role of routine pessary placement prior to planned surgery for symptomatic prolapse in a prospective case-crossover trial where patients scheduled for operative prolapse repair will utilize a pessary preoperatively. We anticipate that this trial will define the clinical utility of routine preoperative pessary placement, and by shaping patient expectations and increasing preparedness for surgery, we anticipate improving satisfaction and quality of life.

Research Plan

I. Specific Aims:

Pelvic organ prolapse is a highly prevalent issue in adult women and can have a large impact on a woman's quality of life, leading to discomfort, decreased energy and increase social isolation. Notably, the prevalence of prolapse increases with advancing age and it is estimated that the lifetime risk of a woman undergoing surgery for bothersome prolapse is as high as 13%. Likewise, given the present age distribution in the United States, the number of women seeking treatment for this issue in the future will continue to expand. While many women will undergo surgery, preoperative counseling in preparation for surgery is variable. In fact, self-reported patient preparedness for prolapse surgery has been reported as low as 58% in a previous series from a large tertiary care center. This is an important consideration as patient preparedness for surgery is associated with patient satisfaction and symptomatic improvement.

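### Aim 1a hypothesises a strong correlation of PGI-I after pessary and after surgery, but raw percent concordance, the only PGI-I agreement statistic planned, cannot show it

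*Combined protocol and SAP*

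**What the plan says.** The Aim 1a objective in section I (Specific Aims) is "To evaluate concordance of the Patient Global Impression of Improvement Score between vaginal pessary use (assessed prior to surgery) and surgical intervention". The hypothesis attached to it is different: "There is a strong correlation between the self-reported Patient Global Impression of Improvement Score following pessary use and surgery". No coefficient is named and no value is set for what counts as strong.

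The statistics planned for PGI-I are:

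- **C.3 (Outcome Assessment):** "Concordance will be estimated along with a 95% confidence interval". Success is defined as the top two answers on the scale.
- **C.4 (Sample Size Considerations):** "we anticipate an overall concordance of at least 80% between the within patient ratings following pessary use and 6-weeks following surgery", after the seven answers are collapsed to three groups. The target is a 95% CI half-width of 10 points (70.8-90.5%), giving 62 patients.
- **C.5 (analysis paragraph):** "The percent concordant will be calculated along with the corresponding 95% confidence interval".

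C.5 also assigns McNemar's test (dichotomous responses) and Bowker's test (ordinal responses) to differences between the two time points. Lin's coefficient is limited to the questionnaire scores: "The correlation between the two time points for summary scores from validated questionnaires (POPDI-6, PFIQ-7, OABSS) will be assessed" with it. Aim 1b therefore has a statistic that matches its hypothesis. Aim 1a does not.

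**The concern.** Percent concordance mixes two things: whether a woman's pessary answer is related to her surgical answer, and how many women do well on both treatments. If nearly everyone is much better both times, concordance is high even when the pessary answer says nothing about the surgical one.

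The trial's title is "Prediction of postsurgical symptomatic outcomes with preoperative pessary use". For counselling, the useful question is whether women who do well with the pessary do better after surgery than women who do not. Under the plan as written, the anticipated result of about 80% could be reported, and read as support for the hypothesis, when there is almost no relationship. The planned PGI-I statistics would not reveal which case had occurred.

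**Working it through.** **1. The plan's own figure.** From C.4: anticipated concordance 0.80, half-width 0.10, 95% confidence.

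n = 1.96² × 0.80 × 0.20 / 0.10² = 61.5, rounded up to 62. The Wald interval for 50/62 = 0.806 is 0.806 ± 1.96 × √(0.806 × 0.194 / 62) = 0.708 to 0.905. Both stated figures reproduce.

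**2. Chance agreement.** Let a and b be the success proportions after pessary and after surgery. The documents give neither, so the values below are assumptions. For success or not:

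- chance agreement pe = ab + (1−a)(1−b)
- kappa = (po − pe) / (1 − pe), with observed agreement po = 0.80

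| Pessary / surgery success | pe | kappa at 80% observed |
|---|---|---|
| 70% / 70% | 0.58 | 0.52 |
| 80% / 80% | 0.68 | 0.38 |
| 80% / 90% | 0.74 | 0.23 |
| 85% / 90% | 0.78 | 0.09 |
| 90% / 90% | 0.82 | −0.11 |

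Setting pe = 0.80 with a = b gives a = (1 + √0.6)/2 = 0.887. Two unrelated ratings, each with about 89% success, would agree 80% of the time. If two unrelated ratings each had 90% success, the probability of at least 50 concordant pairs in 62 is 0.68.

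**3. Two tables with the same planned result.** Cells are: success at both, pessary only, surgery only, neither. No woman is placed in the worst category. The three-category kappa, linearly weighted or not, then equals the two-category one, and Bowker's test reduces to McNemar's.

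| | Table A: 49, 6, 6, 1 | Table B: 31, 6, 6, 19 |
|---|---|---|
| Concordant | 50/62 = 80.6% | 50/62 = 80.6% |
| 95% CI | 70.8-90.5% | 70.8-90.5% |
| McNemar (6−6)²/12 | 0, p = 1.00 | 0, p = 1.00 |
| Success at each time | 55/62 = 88.7% | 37/62 = 59.7% |
| Chance agreement | 0.800 | 0.519 |
| Kappa (large-sample SE) | 0.03 (0.139) | 0.60 (0.104) |
| Kappa 95% CI | −0.24 to 0.31 | 0.39 to 0.80 |
| Surgical success after pessary success | 49/55 = 89% | 31/37 = 84% |
| Surgical success after pessary non-success | 6/7 = 86% | 6/25 = 24% |

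The first three rows are the PGI-I agreement and difference results that the plan would produce, and they are identical. The remaining rows, which bear on the hypothesis, are not planned.

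**4. The other direction.** Suppose 31 women move from the middle group after pessary to the top group after surgery, and 31 move from the bottom group to the middle. Concordance is 0%, yet the rank correlation is 1.0. Low concordance therefore does not refute the hypothesis either.

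**The case against.** The strongest reply is that the plan is consistent with its objective. Aim 1a sets out to evaluate concordance, and C.3, C.4 and C.5 all follow through. The mismatch lies in the hypothesis sentence, and Aim 1b uses the same wording, so the authors may use concordance and correlation loosely. C.1 describes the goal as comparative efficacy, and how often a woman's two results match is a legitimate thing to tell patients. This is why percent concordance should stay as the sized estimate. It does not rescue the hypothesis as written. Sections I and II also argue that pessary response may show which symptoms surgery can correct, which is a claim about association.

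The size of the problem is also assumed. Table A, with 89% success at both times, is close to a worst case; at 70% success, 80% concordance goes with a kappa of 0.52. That is fair: the gap is certain, but its practical size is not known in advance.

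McNemar's and Bowker's tests require the cross-table, so the missing quantities could be derived from it. The plan does not commit to reporting that table.

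Finally, kappa itself depends on the success rates, and the added estimates are weakest where the problem is worst. In Table A the difference in surgical success is 3 points, with a 95% CI of −24 to 31. That stands, and it is why the fix reports conditional success rates beside kappa, each with its interval.

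**Conclusion.** The concern holds. The primary hypothesis for PGI-I is about correlation, and no planned PGI-I statistic measures association or corrects agreement for chance. The anticipated result (80.6%, CI 70.8-90.5%) fits a kappa of 0.03 as well as one of 0.60, depending on success rates that the documents do not give. The problem is serious if success is near 90% at both times and milder at 70% or below. The 62-patient calculation and the concordance estimate are sound, and McNemar's and Bowker's tests are suited to the purpose C.5 gives them. This should be corrected, but it does not invalidate the design.

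**What to change.** In C.5, keep percent concordance as the sized estimate and keep McNemar's and Bowker's tests for differences between time points. Add wording such as:

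> For Aim 1a the full PGI-I cross-table (post-pessary by post-surgery) will be shown with chance-expected agreement and linearly weighted kappa with 95% CI. Surgical success will be reported among women with and without pessary success, with the difference and 95% CI. The conclusion on the strong-correlation hypothesis will rest on these as well as on percent concordance.

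The same text should name three things: the scale used for kappa (seven points or the three groups in C.4), the postoperative rating used (Aim 1a says 3 months, C.4 says 6 weeks), and what will count as strong. Rewording the hypothesis as one about concordance would remove the literal mismatch, but it would leave the question of prediction unanswered.

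The cost is a few sentences and a few lines of analysis on data already scheduled, with no new visits or patients. The headline may look less favourable, and the added estimates will be imprecise. Assuming surgical success of 90% after pessary success and 80% otherwise, the half-width of the difference is 1.96 × √(0.9 × 0.1/n₁ + 0.8 × 0.2/n₀), where n₁ and n₀ are the numbers with and without pessary success:

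| Pessary success | n = 62 | n = 84 |
|---|---|---|
| 80% | n₀ ≈ 12, ±24 points | n₀ ≈ 17, ±20 points |
| 90% | n₀ ≈ 6, ±32 points | n₀ ≈ 8, ±28 points |

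The kappa half-width at n = 62 is about 0.20 (Table B) to 0.27 (Table A).
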